8.3 Immune Evaluations

Immune evaluations (IEs) will be conducted as delineated in **Table 1**. Baseline serum and cells will be aliquoted from the pheresis. Blood draws (4 green top tubes containing approximately 30-40 milliliters of anti-coagulated blood and 1 red top tube containing 8 milliliters of serum) at each time point. Immunologic Control samples from non-transfused hospitalized patients will be obtained from the UVA COVID-19 Biorepository. Permission has been obtained from the Biorepository Committee.

9.0 STATISTICAL CONSIDERATIONS

9.1 Power calculation

Twenty-nine evaluable patients will have 80% power to declare a significant decrease in ICU admissions from a historical control of 50% of hospitalized patients to 25% with a two-sided type I error of 0.05 (reject ICU admission rate=50% if only 8 or less patients are admitted to ICU among 29 evaluable patients).

Data analysis: For categorical clinical endpoints, frequency with percentage will be summarized. For the quantitative clinical variables and immune response variables measured in this objective, we will produce summary statistics (including means, medians, and standard deviations) for data at pre- and post-CIP infusions. Subsequent analyses will compare the serologic and neutralization antibody titers for anti-SARS-COV-2 antibodies and immune response variables (after a suitable data transformation to improve normal distribution, if necessary) pre- and post-treatment using a paired t-test (or Wilcoxon sign ranked test if the data are not approximately normally distributed). The level of each measured immune biomarker measured at the follow-up time points will be plotted to visually show the change of immune responses over time. To explore whether immune responses at pre- or peak improvement at post-CIP infusions associate with clinical endpoints (such as ICU admission, intubation), logistic regression for binary endpoints and Cox regression for time to event endpoints will be used to analyze each measured immune biomarker respectively. These effects will be compared to biospecimen from non-transfused immunologic controls. Analyses will adjust for other covariates such as age and co-morbidities. No

multiplicity adjustment is planned due to the nature of being exploratory. A two-sided p-value of < 0.05 will be considered significant.

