2.3 Study Design

This is a single arm phase II trial to assess preliminary efficacy and confirm safety of infusions of anti-SARS-CoV-2 convalescent plasma in hospitalized patients with acute respiratory symptoms **with or without** confirmed interstitial COVID-19 pneumonia by CXR or chest CT. A total of 29 eligible subjects will be enrolled to receive high titer anti-SARS-CoV-2 plasma. Participants will be compared to a historical control group via retrospective chart review.

In addition, the following Immunologic Controls will be used to meet secondary objectives described above:

1. PBMCs with 5-10 million cryopreserved cells per specimen will be obtained from the prospective COVID 19 Biorepository (2 timepoints per patient t (60 specimens total) and assessed for cellular and humoral immune responses.
2. Serum or plasma 500 UI each from up to 50 patients in the Covid-19 Biorepository will be collected (2 timepoints from each patient) (100 total specimens) will be evaluated for antibody and cytokine responses.

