7.0 STATISTICAL CONSIDERATIONS

7.1 Statistical Analyses

Twenty-nine evaluable patients will have 80% power to declare a significant decrease in ICU admissions from a historical control of 50% of hospitalized patients to 25% with a two-sided type I error of 0.05 (reject ICU admission rate=50% if only 8 or less patients are admitted to ICU among 29 evaluable patients). The historic control group will consist of 29 patients who are gender and age (within 5 years) matched.

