10.9 Subject Status Definitions

- Enrolled: All subjects who sign an informed consent will be considered enrolled on the study. All subjects consented on the study must be entered into Clinical Trials Office Database.
- Screen Failure: A subject who is withdrawn or discontinues from study screening prior to being on study is considered a screen failure. Screen failures are not considered a study accrual and will be replaced. Note: The IRB defines any individual that has signed an informed consent as an enrollment in this study and so screen failures should be reported to the IRB with enrollment numbers.
- On-Study: A subject is considered on-study on the date when the study team has confirmed the subject has met all of the inclusion and none of the exclusion criteria, and the treating physician/surgeon or study PI has signed off on the confirmation.
- On-Treatment: A subject is considered on-treatment on the date that they receive the first study treatment. A subject who is withdrawn or discontinues from the study after receiving at least 1 infusion is considered a discontinuation and will not be replaced.
- On Follow-up: A subject is considered on follow-up on the date that they have met any of the criteria in section 4.0.
- Off-Study: A subject is considered off-study if they are removed from the study for any of the reasons listed in section 4.0 or if they have completed all study assessments through follow-up.
- Immunologic Controls: A subject for whom biospecimen is obtained from the COVID-19 Biorepository.

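### The printed rule of 8 or fewer ICU admissions among 29 has 71% power at the target rate, not the stated 80%

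*Combined protocol and SAP*

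**What the plan says.** Section 7.1 (Statistical Analyses) and section 9.1 (Power calculation) carry the same sample-size statement. It opens "Twenty-nine evaluable patients will have 80% power to declare a significant decrease in ICU admissions", takes 50% as the historical rate and 25% as the target, and works "with a two-sided type I error of 0.05". A parenthesis then fixes the rejection region: "reject ICU admission rate=50% if only 8 or less patients are admitted to ICU among 29 evaluable patients".

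Neither section names the test, says whether the power is approximate or exact, or gives the attained alpha. The data-analysis text in 9.1 summarises categorical clinical endpoints by frequency and percentage and sets a general two-sided significance level of 0.05. It names no test of ICU transfer against 50%. No allowance for loss of evaluable patients is stated, and section 10.9 says that a treated patient who leaves "is considered a discontinuation and will not be replaced".

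**The concern.** One sentence fixes six quantities: the number of patients, the null rate, the target rate, alpha, the power and the cut-off. The first three and the cut-off already determine both the power and the type I error, so the stated 80% either follows from them or is wrong.

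This is the only efficacy criterion the plan states for a primary endpoint; the rules in section 15 concern safety. If its power is overstated, a result that misses the cut-off will look like stronger evidence against the targeted effect than it is. If the power and the cut-off come from different tests, one possible outcome (9 of 29) is a success under one test and a failure under the other, and the plan does not say which applies.

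**Working it through.** **Inputs (sections 7.1 and 9.1).** n = 29; p0 = 0.50, treated as a known constant; p1 = 0.25; two-sided alpha 0.05; stated power 80%; reject if X ≤ 8, where X is the number admitted to ICU.

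**Step 1. Reproduce the plan's 80%.** One-sample normal approximation, null variance under p0, alternative variance under p1, no continuity correction:

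- Required n = [(1.96 × √(0.5 × 0.5) + 0.8416 × √(0.25 × 0.75)) / 0.25]² = [(1.96 × 0.5 + 0.8416 × 0.4330) / 0.25]² = 28.92, rounded up to 29.
- Power at 29 = Φ[(0.25 × √29 − 1.96 × 0.5) / 0.4330] = Φ(0.846) = 80.1%.

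So 29 and 80% agree with each other under this formula.

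**Step 2. Power of the printed rule.** X is binomial with n = 29:

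- Power = P(X ≤ 8 | 29, 0.25) = 0.7125.
- Lower-tail type I error = P(X ≤ 8 | 29, 0.50) = 0.01206; doubled, 0.0241.
- Shortfall = 80.0 − 71.3 = 8.7 percentage points. Type II error = 28.7% against 20%.

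The power figure does not depend on the choice of test, sidedness or alpha, because the rule itself is the rejection region.

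**Step 3. Would another cut-off at n = 29 give both properties?**

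| Rule | Exact alpha, doubled tail | Exact power at 25% | z-test at the cut-off |
|---|---|---|---|
| X ≤ 8 | 0.0241 | 71.3% | z = −2.41, p = 0.016 |
| X ≤ 9 | 0.0614 | 83.4% | z = −2.04, p = 0.041 |

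Under the exact equal-tailed test, 8 is the correct cut-off and 9 exceeds 0.05. Under the normal-approximation test that produced the 80%, 9 of 29 is also significant. The stated power therefore belongs to one test and the printed cut-off to another. At a true rate of 25%, exactly 9 admissions has probability 0.8337 − 0.7125 = 0.121, so the disputed outcome is not remote.

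**Step 4. Where the printed rule reaches 80%.** P(X ≤ 8 | 29, p) is 83.1% at p = 0.22, 79.4% at p = 0.23 and 75.5% at p = 0.24. It equals 80% at p = 0.2285, about 22.9%.

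**Step 5. Nearby evaluable numbers, exact two-sided test.**

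| Evaluable n | Largest cut-off with doubled alpha ≤ 0.05 | Attained alpha | Power at 25% |
|---|---|---|---|
| 27 | 7 | 0.019 | 64.3% |
| 28 | 8 | 0.036 | 75.0% |
| 29 | 8 | 0.024 | 71.3% |
| 30 | 9 | 0.043 | 80.3% |
| 31 | 9 | 0.029 | 77.1% |

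Thirty is the smallest number that meets both targets exactly, but power falls below 80% again at 31, 32 and 34.

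**The case against.** The best defence is that 29 and 80% are not a slip. They follow from a standard large-sample formula, and the plan does not commit itself to an exact test. On that reading the cut-off is the wrong figure: it should be 9, where the z-test gives p = 0.041 and the exact power is 83.4%. This shows where the numbers came from, and it stands as a second way to reconcile them. It does not rescue the sentence, which attaches 80% to a cut-off of 8. It also has a price, because a cut-off of 9 has an exact doubled alpha of 0.061, above the stated 0.05.

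A second defence is that the rule is conservative and that section 2.3 calls the efficacy assessment preliminary. It is true that type I error is not inflated: 0.024 is used out of 0.05. The harm is confined to power.

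A third is that the rule may not be the final analysis at all, since section 7.1 also plans 29 matched controls. The role of those controls is unclear, and 71% would not be the power of a matched comparison. But the plan's power statement is written for the fixed 50% rate, and it should be right for the rule it prints.

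**Conclusion.** The concern holds. The printed rule has 71.3% power at a true ICU admission rate of 25%, 8.7 points below the stated 80%, and its type II error is 28.7% rather than 20%. The attained two-sided alpha is 0.024. The cause is an approximate power paired with an exact cut-off.

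The result rests only on the figures in sections 7.1 and 9.1 and on independent patients with a common admission rate. Like the plan, it takes 50% as known without error. That 8 is the right cut-off and 9 is not rests on the doubled-tail exact test; the 71.3% does not.

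**What to change.** In sections 7.1 and 9.1, in identical words, keep 29 evaluable patients and the cut-off of 8. Name the one-sample exact binomial test, and replace the power claim with: attained two-sided alpha 0.024; power 71% at a true rate of 25%; power 80% at a true rate of about 23%. Because treated patients who discontinue are not replaced, also state how the cut-off is set if the evaluable number is not 29, for example as the largest count with doubled exact alpha no greater than 0.05.

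The cost is wording in two sections and a less favourable power figure. Enrolment does not change.

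If 80% must be kept, 30 evaluable patients with a cut-off of 9 gives exact two-sided alpha 0.043 and power 80.3%. That option has almost no margin and holds only at exactly 30 evaluable. It would also mean changing the 29 in the Summary and in sections 2.3, 5.1, 7.1, 7.2, 9.1 and 9.2, and, if matching stays one to one, adding a control as well as a patient. Restating the power is the simpler course.

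### With about 7 events expected in 29 patients, the adjusted biomarker models in section 9.1 overstate odds ratios, can fail to fit, and give p-values that depend on an unnamed test

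*Combined protocol and SAP*

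**What the plan says.** The data-analysis paragraph of section 9.1 sets out to explore whether immune responses before infusion, or at their peak afterwards, "associate with clinical endpoints (such as ICU admission, intubation" and similar. The method is "logistic regression for binary endpoints and Cox regression for time to event endpoints will be used to analyze each measured immune biomarker respectively". It continues: "Analyses will adjust for other covariates such as age and co-morbidities". It states that no "multiplicity adjustment is planned due to the nature of being exploratory", and closes with "A two-sided p-value of < 0.05 will be considered significant".

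Neither this paragraph nor any other section gives:

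- the number or coding of the co-morbidities, or a limit on covariates
- a penalised or exact method
- a rule for a model that does not converge
- the test behind the p-value (Wald or likelihood ratio)

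Logistic and Cox regression named without qualification are read here as the ordinary maximum-likelihood and partial-likelihood fits.

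No event count is stated for these models. It follows from the design, which opens the section: "Twenty-nine evaluable patients will have 80% power to declare a significant decrease in ICU admissions". The change assumed there is "from a historical control of 50% of hospitalized patients to 25% with a two-sided type I error of 0.05", and the decision rule is to "reject ICU admission rate=50% if only 8 or less patients are admitted to ICU among 29 evaluable patients". Section 7.1 repeats the same design figures.

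**The concern.** Maximum-likelihood logistic regression is biased away from an odds ratio of 1 when there are few events per coefficient. It has no finite solution when the covariates separate events from non-events. The trial's own design figures put these models in that range, and success makes it tighter: a trial that meets the decision rule has at most 8 ICU admissions.

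What is at stake is the credibility of the biomarker-outcome associations. Estimates that converge would look stronger than they are. Some models would yield nothing, with no agreed fallback. The same data could be called significant or not according to which p-value the software prints.

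**Working it through.** **Step 1. The plan's own figure.** One-sample proportion, normal approximation: n = ((1.960 × √(0.5 × 0.5) + 0.842 × √(0.25 × 0.75)) / 0.25)² = 28.9, so 29, with power 80.1%. The stated sample size reproduces. (The exact binomial power of the rule of 8 or fewer is 71.3%. That is a separate matter and is not used below.)

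**Step 2. Events.** These follow from section 9.1.

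- At 25%: 29 × 0.25 = 7.25 (binomial 95% range 3 to 12).
- At 50%: 29 × 0.50 = 14.5.
- Intubations are probably fewer than ICU admissions. The documents give no rate; at an assumed 10%, 29 × 0.10 = 2.9.

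**Step 3. Events per coefficient.** A biomarker, age and one to five co-morbidity terms make 3 to 7 coefficients: 7.25 / 3 = 2.4 down to 7.25 / 7 = 1.0.

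**Step 4. Logistic simulation.** The assumptions, which are not in the documents, are: independent standard normal biomarker and age; log odds ratio 0.5 per SD of age and 0.5 per co-morbidity; binary co-morbidities at 40% prevalence; intercept set for 25% events. The table gives ranges over repeated runs. Run sizes reached 3,000 trials per setting. At 1,500 trials a 10% rate has a standard error of √(0.1 × 0.9 / 1500) = 0.8 points.

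| Co-morbidity terms | 1 | 3 | 5 |
|---|---|---|---|
| No finite estimate (null) | 3-5% | 10-15% | 24-30% |
| Likelihood-ratio rejection (null, nominal 5%) | 7.4-9.1% | 9.4-10.6% | 9.7-10.3% |
| Wald rejection (null, nominal 5%) | 3.1-3.6% | 2.6-2.7% | 1.9-2.2% |
| Median estimate, true OR 2.0, converged fits | 2.3-2.4 | 2.5 | 2.7-2.8 |
| Geometric mean estimate, true OR 2.0 | 2.7 | 3.0-3.1 | 3.5 |

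With five terms and a true odds ratio of 2, the likelihood-ratio test rejects in 35% of trials and the Wald test in 10%.

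**Step 5. Sensitivity.**

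- Age as the only covariate: no finite fit in 0.1-0.4% of trials; median odds ratio 2.1.
- Age plus one co-morbidity count, still by maximum likelihood: no finite fit in 1.6% under the null, median odds ratio 2.2-2.3, likelihood-ratio rejection about 7%, Wald 2.3-2.5%.
- ICU rate 50%, settings otherwise as in step 4: no finite fit in about 0.6-8%, but the median odds ratio is still 2.2-2.7 and likelihood-ratio rejection stays raised.
- Co-morbidities at 15% prevalence (covariate odds ratio 2): no finite fit in 44% with two terms and 57% with three.
- Event rate 10% (30% prevalence, covariate odds ratio 2): 55% with two terms and 70% with three.

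**Step 6. Cox simulation.** 25% events, censoring at the end of follow-up, one to three co-morbidities at 30% prevalence, covariate hazard ratio 2, 1,500 runs. Non-convergence is about 6%, 11% and 15%. A true hazard ratio of 2 is estimated at a median of 2.2, 2.25 and 2.35. Under the null, Wald rejects in 4.7-6.0% and likelihood ratio in 6.7-9.3%.

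**Step 7. The remedy.** Firth-penalised logistic regression under the step 4 settings gives a geometric mean of 2.0-2.1 for a true 2.0 (median about 1.9), false positives of about 3-5%, and an estimate in over 99% of trials. A Firth-penalised Cox model was not simulated.

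**The case against.** Four points can fairly be made on the other side.

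**Exploratory status.** Section 9.1 says these analyses explore, and biomarker-outcome association is not among the endpoints in section 7.3. This stands as a limit on importance. It explains the absence of a multiplicity adjustment, but it does not excuse biased or missing estimates, and the paragraph still sets a significance threshold.

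**False positives.** A reader might infer that the plan will produce excess false positives. The documents do not support that, because no test is named. Logistic Wald tests are conservative, so their cost is lost power, and Cox Wald tests are near nominal. Excess appears only with likelihood-ratio tests.

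**Separation.** A reader might also infer that frequent model failure is certain. It needs several binary co-morbidity terms, uncommon co-morbidities or a rare endpoint. The existing wording would permit a single co-morbidity score, which removes most of it. Some inflation of the odds ratio and of likelihood-ratio rejection remains even then, so restricting covariates is not the whole answer.

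**Event count.** Seven is conditional on the 25% rate. At 50% separation becomes much rarer, yet inflation persists. Pooling the non-transfused immunologic controls into the models might raise the count, but section 9.1 speaks only of comparing effects with those specimens.

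**Conclusion.** The point holds in a limited form. At the design ICU rate, the adjusted logistic models in section 9.1 would typically report a true odds ratio of 2.0 as about 2.3 to 2.8. They would have no finite estimate in about 3-5% of trials with one co-morbidity term and 24-30% with five. Their p-values would be too liberal by likelihood ratio (about 7-10%) or too conservative by Wald (about 2-4%). Cox models share the problem to a lesser degree, with a median hazard ratio of about 2.2 to 2.35 for a true 2.

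The sizes rest on assumed covariate number, prevalence and effects, and on independent, normally distributed biomarker and age. The direction of the bias does not depend on the 25% rate. Nothing here bears on the primary ICU test or its decision rule, and it would be wrong to read the point as a threat to the main result. It is worth correcting because the plan names a method poorly suited to its own expected data when a better one is readily available.

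**What to change.** In the data-analysis paragraph of section 9.1:

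1. Replace the logistic models with Firth-penalised logistic regression, and use Firth-penalised Cox regression where events are few.
2. Take p-values and intervals from the penalised profile likelihood. This also settles which test applies.
3. Limit adjustment to age plus one co-morbidity count, and list in advance the conditions that enter the count.
4. Report the unadjusted estimate and the number of events beside each adjusted estimate.

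The cost is SAP wording and standard software; no further patients or data are needed. There are small downsides. A single count controls confounding less finely than separate terms, and fewer biomarkers will be nominally significant than with ordinary likelihood-ratio tests. Even after the change there are only about 2.4 events per coefficient (7.25 / 3), so intervals will be wide and the results remain exploratory.

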Drug: Pathogen reduced SARS-CoV-2 convalescent plasma (1-2 units; 2 units are preferable but a single unit is allowable in the setting of safety/time/resource/etc concerns; ~200 mL each for a total of upto ~400 mls) given preferably in one day, but allowable to be given over 2 days if clinical circumstances delay infusions in 1 day), with titer to be determined after the unit has been infused.

Directed Donor Plasma Units: Healthy donors who have recovered from COVID-19 infection 21 days after symptom resolution will undergo a donor eligibility questionnaire. If eligible, blood will be drawn for ABO typing, HLA antibodies, and infectious disease panel screening. One additional red top tube will draw and sent to the [name] laboratory at UVA to test for levels of IgG anti-COVID-19 spike protein. No OP or NP PCR testing will be performed at day 21 given that donation will occur at day 28 or after. If the donor is eligible and matched, they will be called back to donate plasma at the ARC on day 28 after symptom resolution or later. The ARC or other local facility will collect blood for ABO, HLA, and infectious disease panel screening obtained via Emergency Use Authorization.

Immune Evaluations: Immune evaluations will be performed to determine if infusions of immune plasma enhance the development of anti-COVID-19 immune responses: peripheral blood mononuclear cells (PBMC) will be cryopreserved for measurements of specific anti-COVID-19 IFN-γ ELISpots, single cell high-dimensional immunophenotyping by mass cytometry and RNA-Seq; specific serum IgG, IgM and IgA antibodies COVID-19 and levels of Th₁/Th₂ serum cytokines at the designated time points at 0, 14, and 28 days after CIP infusion.

i. List of Abbreviations

ADR Adverse Drug Reaction

² Measured by an anti-SARS-CoV-2 ELISA and serum antibody titer to SARS-CoV-2.

ADE	Antibody-mediated enhancement of infection
BP	Blood pressure
CIP	Convalescent Immune Plasma
CTCAE	Common Terminology Criteria for Adverse Events
DBP	Diastolic Blood Pressure
DLT	Dose limiting Toxicity
DSMB	Data and Safety Monitoring Board
ECG/EKG	Electrocardiogram
EUA	Emergency Use Authorization
FDA	Food and Drug Administration
GCP	Good Clinical Practice
HBV	Hepatitis B virus
HCV	Hepatitis C virus
HIV	Human immunodeficiency virus
HTLV	Human T-cell lymphotropic virus
IB	Investigator’s Brochure
ICF	Informed Consent (Informed Consent Form)
ICH	International Conference on Harmonization
ICU	Intensive Care Unit
IEs	Immune Evaluations

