10.8 Immune Evaluations

Immune evaluations (IEs) will be conducted as delineated in Table 1. Baseline serum and cells will be aliquoted from the pheresis. Blood draws (4 green top tubes containing approximately 50 mL of anti-coagulated blood and 1 red top tube containing 8 mL of serum) will be collected at designated time points at 0, 7, 14, and 28 days after CIP infusion. All patients receiving any dose of study treatment should be assessed for immune markers. Evaluations will include:

- Serum cytokine/chemokine levels
- Phenotyping of T cells and T cell subpopulations, TCR repertoire analysis, monocyte, B cells, and NK cell by flow cytometry.
- Cytotoxic activity and IFN γ production in PBMC populations. An immune response will be defined as a 30 IFN γ Elispots per million cells plated above the background of unstimulated spontaneous IFN γ Elispots per million cells plated.
- Additional assays may be performed on available samples to evaluate Th₁/Th₂ responses in single cell RNA sequencing on selected samples.

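### Section 9.1 calls the immune biomarker analyses exploratory and leaves them uncorrected, yet labels any p < 0.05 significant, with no false discovery control for the high-dimensional assays

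*Combined protocol and SAP*

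**What the plan says.** The data analysis paragraph of Section 9.1 sets out two kinds of immune test. Titers and immune response variables are compared "pre- and post-treatment using a paired t-test (or Wilcoxon sign ranked test if the data are not approximately normally distributed"). Association models are then introduced with the words "To explore whether immune responses at pre- or peak improvement at post-CIP infusions associate with clinical endpoints": logistic regression for binary endpoints and Cox regression for times to event, which "will be used to analyze each measured immune biomarker respectively". ICU admission and intubation are given as example endpoints. A comparison with non-transfused immunologic controls and adjustment for age and co-morbidities follow.

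The paragraph ends by stating that no "multiplicity adjustment is planned due to the nature of being exploratory. A two-sided p-value of < 0.05 will be considered significant".

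The assays are listed elsewhere. The Immune Evaluations paragraph of the Summary names "single cell high-dimensional immunophenotyping by mass cytometry and RNA-Seq", with ELISpots, antibody classes and serum cytokines. Section 10.8 adds "Phenotyping of T cells and T cell subpopulations, TCR repertoire analysis, monocyte, B cells, and NK cell by flow cytometry" and serum cytokines and chemokines. It also makes further assays optional and limits single-cell RNA sequencing to selected samples.

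Section 7.3.2 lists cellular and humoral responses as secondary endpoints. No section gives the number of biomarkers or tests, names a lead immune measure, or plans a false discovery rate.

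**The concern.** The last two sentences of the paragraph pull against each other. If the work only generates hypotheses, leaving p-values uncorrected is defensible, because nothing is being declared. Once any p below 0.05 earns the word *significant*, the analysis declares results, and the exploratory label no longer excuses the missing error control.

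This matters most for assays that return many features per sample. Applied to each feature separately, a 0.05 rule yields a steady supply of chance findings, and the plan offers nothing to separate them from real ones. The Summary says the immune evaluations are meant to find out whether plasma enhances anti-COVID-19 immunity, so readers may take a feature labelled significant as an answer to that question.

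**Working it through.** **The plan's own figures.** There is no plan figure on this point to reproduce, because no number of biomarker tests is stated. The only sizing figure, 29 patients for 80% power, concerns ICU admission. The normal approximation reproduces it: ((1.96 × 0.5 + 0.842 × √(0.25 × 0.75)) / 0.25)² = 28.9, so 29. (The exact power of the stated rule, 8 or fewer of 29, is 71.3%; that is a separate matter.) That rule uses ICU counts alone, so no biomarker result enters it.

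**Inputs from the documents.** Per-test level 0.05, two-sided; no adjustment; one model per biomarker (all Section 9.1).

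**Assumed inputs.** The number of tests m, the share of them that are truly null (π0), and the power per test. The documents give none of these, so ranges are shown.

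**1. Expected false positives** = 0.05 × number of null tests. Correlation between markers does not change this.

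- 20 null tests: 1
- 50: 2.5
- 100: 5
- 1,000: 50

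**2. Chance of at least one false positive** if all m tests are null and independent = 1 − 0.95^m. Positive correlation between markers lowers it.

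- m = 10: 40.1%
- m = 14: 51.2%
- m = 20: 64.2%
- m = 50: 92.3%
- m = 100: 99.4%

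To give a sense of scale, suppose the baseline value and the peak improvement of each marker are each related to the two example endpoints. That is 2 × 2 = 4 tests per marker, so 25 markers give 100 tests. These would be correlated: the expected count of 5 stands if all are null, but 99.4% would be too high.

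**3. Share of declared findings that are false**, approximately π0 × 0.05 / (π0 × 0.05 + (1 − π0) × power).

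- Power 80%: 6% at π0 = 0.5, 20% at 0.8, 36% at 0.9, 54% at 0.95, 86% at 0.99
- Power 30%: 14%, 40%, 60%, 76% and 94% at the same values

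The share passes one half when π0 exceeds power / (power + 0.05): 0.80 at 20% power, 0.857 at 30%, 0.909 at 50% and 0.941 at 80%.

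**4. Is that power range reasonable for 29 patients?** For an unadjusted logistic model, power is about Φ(√(29 × p × (1 − p)) × ln OR − 1.96), where p is the ICU rate. With an odds ratio of 2 per standard deviation this is 37% at p = 0.25 and 46% at p = 0.50, the protocol's two ICU rates. A paired t-test with a standardised change of 0.5 has 74% power. These effect sizes are illustrative; the documents give none.

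**The case against.** The plan is open about its choice. It gives the exploratory purpose as the reason for not adjusting, and unadjusted testing that is plainly labelled hypothesis-generating is accepted practice. The immune measures are secondary endpoints, and the ICU rule does not depend on them. All of this stands, and it limits the point to the significance label and the missing false discovery control.

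It is also fair to say that the plan never states that each transcript, cell cluster or T-cell clone is a biomarker to be tested at 0.05. That is inferred from the plan to analyse each measured biomarker. Nor is there a test at every visit: follow-up levels are to be plotted, the association models use baseline or peak values, and Section 9.4 makes the comparison of titers across days descriptive. Counts obtained by multiplying markers by visits, or by assuming a transcriptome-wide test, therefore lack support in the text. The concern depends on feature-level testing being done, which the wording allows and nothing rules out.

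A reader might go further and infer that most declared immune findings would be chance. The documents do not support that. It needs a null share above about 0.80 to 0.94, depending on power, and they give neither the null share nor the number of tests. It is plausible for a broad feature screen and unlikely for pre/post titers, where real change is expected after antibody infusion and during infection.

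Finally, false discovery control addresses chance only. In a single-arm comparison during acute infection, a real change may reflect natural recovery, and a q-value cannot show otherwise.

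**Conclusion.** The point holds in a limited form. Section 9.1 attaches a significance label to uncorrected tests that it calls exploratory, and it plans no false discovery control although high-dimensional assays are listed. Followed literally in a feature-level analysis, the rule labels about 5% of true nulls significant. At 100 null tests that means 5 expected, and a 99.4% chance of at least one under independence.

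The size rests on assumed test counts and on features being tested one by one. Over the null shares and powers shown, the false share of declared findings runs from 6% to 94%, so no single value can be claimed. The primary ICU decision is untouched. This is an inexpensive improvement to the analysis plan and does not put the trial's main conclusion in doubt.

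**What to change.** Replace the closing sentence of the Section 9.1 data analysis paragraph with two rules.

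- **Feature-level analyses of high-dimensional assays** (RNA-Seq, mass and flow cytometry, TCR repertoire, multiplex cytokines): report Benjamini-Hochberg q-values within each assay and each type of analysis (pre/post change, or association with a clinical endpoint). Call only q < 0.05 a finding.
- **Other exploratory immune tests:** report estimates with 95% intervals and nominal p-values labelled hypothesis-generating, without the word *significant*. For titers this also brings Section 9.1 closer to the descriptive analysis in Section 9.4.

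The ICU test keeps the two-sided 0.05 level stated with the power calculation.

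The cost is a revision of SAP wording and a small amount of programming, including a record of which tests make up each family. No extra patients, samples or visits are needed. The downside is fewer declared findings.
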